### 8.1.8 End of Treatment and Extended Follow-up Period

**Table 25** Schedule of Assessments - End of Treatment and Extended Follow-up Period

Assessments/procedures a	End of Treatment b	42 -Day (+ 14 days) Safety Follow-Up c	Extended Safety Follow-up (after the last dose)	Details in Section/Appendix
	± 3 days	After the last dose (± 3 days)	Every 3 months (± 2 weeks) for 2 years then every 6 months for 3 years	
Subsequent anti-cancer treatment	X	X	X	9.4.2
AE monitoring	X	X	X d	8.5
Concomitant medications and procedures	X	X		6.6
Haematology (whole blood) with blood smear (pathology)	X	X	X	8.4.4
Clinical chemistry (serum or plasma)	X	X	X	8.4.4
Thyroid panel		X		8.4.4
Urinalysis		X		8.4.4
Pregnancy test (blood or urine, in accordance with institutional practice)	X			8.4.4
Complete physical examination	X			8.4.1
Symptom-directed physical examination		X		8.4.1
ECOG Performance Status	X	X		8.4.5
Weight	X			8.4.1
Ophthalmologic examination	X			8.4.6.2
CT or MRI for RECIST 1.1 Response Assessments	X d		X e	8.2
Serum for tumour marker measurement (e.g., CA-19-9, CEA, etc.) g	X		X h	8.8.1.3
Blood for TCR analysis	X		X	8.8.1.1

ADA, anti-drug antibody; AE, adverse event; CA-19-9, carbohydrate antigen-19-9; CEA, carcinoembryonic antigen; CT, computed tomography; ctDNA, circulating tumour DNA; ECOG, Eastern Cooperative Oncology Group; MRI, magnetic resonance imaging; PK, pharmacokinetics; RECIST, Response Evaluation Criteria in Solid Tumours; RNA, ribonucleic acid; TCR, T-cell receptor.

**a** If clinically indicated, any procedure or assessment may be conducted as an unscheduled visit.

**b** The End of Treatment visit should be conducted within 7 days of the decision to permanently discontinue treatment with  $[^{225}\text{Ac}]$ -FPI-2068.

The Follow-up Visits should be scheduled within CSP-defined timeframe (e.g., 42-56 days) based on the date of the last dose of IMP.

d Only related AEs to be collected in the Extended Follow-Up Period.

Only related AEs to be collected in the Extended Follow Up Period.

### 8.1.9 PK, ECG, and Biomarker Sample Timepoints: Part A (Dose Exploration with Unlabelled bsAb)

**Table 26 PK, ECG, and Biomarker Sample Timepoints: Part A (Dose Exploration with Unlabelled bsAb)**

Visit/timepoint	PK	Triplet 12-lead ECG a	Blood for RNA and TCR analysis	Plasma for ctDNA analysis	ADA samples
Details in Section/Appendix	8.7.1	8.4.3	8.8.1.1	8.8.1.2	8.7.2
General Screening		During visit day		During visit day	
[In]-FPI-2107 Imaging Screening Period					
Day of [  In]-FPI-2107 administration	Predose [  In]-FPI-2107 injection (within 2 h prior)	X	X	X	X
	End of [  In]-FPI-2107 injection	+ 5 min	X		
	1 hr post injection	± 10 min	X		
	2 h post injection	± 15 min	X		
	4 h post injection	± 30 min	X		
	8 h post injection b	± 30 min c	X		
Planar scintigraphy and SPECT/CT timepoints	24 h (± 6 h) post injection	Within 2 h prior	X		
	48 h (± 6 h) post injection	Within 2 h prior	X		
	72-96 h (± 6 h) post injection	Within 2 h prior	X		
28-day Safety Visit d					X
Screening Period with predose FPI-2053 followed by [In]-FPI-2107					
Day of [  In]-FPI-2107	Predose FPI-2053 administration (within 2 h prior)	X	X	X	X

Visit/timepoint		PK	TriPLICATE 12-lead ECG a	Blood for RNA and TCR analysis	Plasma for ctDNA analysis	ADA samples
administration	End of FPI-2053 administration	+ 5 min	X			
	Predose [  In]-FPI-2107 administration	- 5 min	X			
	End of [  In]-FPI-2107 administration	+ 5 min	X			
	1 hr post administration	± 10 min	X			
	2 h post administration	± 15 min	X			
	4 h post administration	± 30 min	X			
	8 h post administration b	± 30 min c	X			
Planar scintigraphy and SPECT/CT timepoints	24 h (± 6 h) post injection	Within 2 h prior	X			
	48 h (± 6 h) post injection	Within 2 h prior	X			
	72-96 h (± 6 h) post injection	Within 2 h prior	X			
Cycle 1 – Treatment Period predose FPI-2053 followed by [Ac]-FPI-2068						
Day of [  Ac]-FPI-2068 administration	Predose FPI-2053 administration (within 2 h prior)	X	X	X	X	X
	End of FPI-2053 administration	+ 5 min	X			
	Predose [  Ac]-FPI-2068 administration	- 5 min	X			
	End of [  Ac]-FPI-2068	+ 5 min	X			

Visit/timepoint	PK	TriPLICATE 12-lead ECG a	Blood for RNA and TCR analysis	Plasma for ctDNA analysis	ADA samples
administration					
	1 hr post administration	± 10 min	X		
	2 h post administration	± 15 min	X		
	4 h post administration	± 30 min	X		
	8 h post administration b	± 30 min	X		
Day 8 (7 days [± 6 h] post injection)	During visit day	During visit day			X
Day 15 (14 days [± 2 days] post injection)	During visit day	During visit day	During visit day	During visit day	
Day 22 (21 days [± 2 days] post injection)	During visit day	During visit day			X
Day 29 (28 days [± 3 days] post injection)	During visit day	During visit day			
Day 57 (56 days [± 3 days] post injection, if Cycle 2 is delayed)	During visit day	During visit day	X c	X c	X c
Cycles 2 and beyond Treatment Period					
Day of [  Ac]-FPI-2068 administration	Predose FPI-2053 administration (within 2 h prior)	X	X	X	X
	End of FPI-2053 administration	+ 5 min	X		
	Predose [  Ac]-FPI-2068 administration	- 5 min	X		
	End of [  Ac]-FPI-2068	+ 5 min	X		

Visit/timepoint	PK	TriPLICATE 12-lead ECG a	BLOOD for RNA and TCR analysis	Plasma for ctDNA analysis	ADA samples
administration					
Day 15 (14 days [ $\pm$ 2 days] post injection)			During visit day	During visit day	
Day 57 (56 days [ $\pm$ 3 days] post injection, if next cycle is delayed)			X c	X c	X c

ADA, anti-drug antibody; bsAb, bispecific monovalent antibody; CT, computed tomography; ctDNA, circulating tumour DNA; ECG, electrocardiogram; PK, pharmacokinetics; RNA, ribonucleic acid; SPECT, single-photon emission computed tomography; TCR, T-cell receptor.

a ECG may be performed, if clinically indicated, at any other visit/timepoint. ECGs must be performed prior to collection of the PK sample at the same timepoint.

b Not required initially, but if early PK data indicates that it is necessary, the 8-hour PK timepoint will be collected.

c If 8 h post injection PK sample is drawn.

d The 28 or 42-day (+ 14 days) Safety Visit only occurs if the participant does not proceed to the treatment phase (i.e., only receives FPI-2053 and [In]-FPI-2107).

e Blood samples for RNA, ctDNA, and ADA assessments at End of Treatment taken only if participant does not progress to next cycle.

### 8.1.10 PK, ECG, and Biomarker Time Points: Part B (Hot Dose Escalation with Unlabelled bsAb)

**Table 27 PK, ECG, and Biomarker Time Points: Part B (Hot Dose Escalation with Unlabelled bsAb)**

Visit/timepoint	PK	Triplicate 12-lead ECG a	Blood for RNA and TCR analysis	Plasma for ctDNA analysis	ADA samples
Details in Section/Appendix	8.7.1	8.4.3	8.8.1.1	8.8.1.2	8.7.2
General Screening		During visit day		During visit day	
Screening Period with predose FPI-2053 followed by [In]-FPI-2107					
Day of [  In]-FPI-2107	Predose FPI-2053 administration (within 2 h prior)	X	X	X	X
	End of FPI-2053 administration	+ 5 min	X		
	Predose [  Ac]-FPI-2107 administration	- 5 min	X		
	End of [  In]-FPI-2107 administration	+ 5 min	X		
	1 hr post administration	± 10 min	X		
	2 h post administration	± 15 min	X		
	4 h post administration	± 30 min	X		
	8 h post administration b	± 30 min c	X		
Planar scintigraphy and SPECT/CT timepoints	24 h (± 6 h) post injection	Within 2 h prior	X		
	48 h (± 6 h) post injection	Within 2 h prior	X		
	72-96 h (± 6 h) post injection	Within 2 h prior	X		
28-day Safety Visit d					X
Cycle 1 – Treatment Period with predose FPI-2053 followed by [Ac]-FPI-2068					
Day of [  Ac]-FPI-2068 Injection	Predose FPI-2053 (within 2 h prior)	X	X	X	X
	End of FPI-2053 administration	+ 5 min	X		
	Predose [  Ac]-FPI-2068	- 5 min	X		

Visit/timepoint		PK	Triplet 12-lead ECG a	Blood for RNA and TCR analysis	Plasma for ctDNA analysis	ADA samples
End of [  Ac]-FPI-2068 administration	End of [  Ac]-FPI-2068 administration	+ 5 min	X			
	1 h post administration	± 10 min	X			
	2 h post administration	± 15 min	X			
	4 h post administration	± 30 min	X			
	8 h post administration b	± 30 min c	X c			
Day 8 (7 days [± 6 h] post injection)	During visit day	During visit day				X
Day 15 (14 days [± 2 days] post injection)	During visit day	During visit day	During visit day	During visit day		
Day 22 (21 days [± 2 days] post injection)	During visit day	During visit day				X
Day 29 (28 days [± 3 days] post injection)	During visit day	During visit day				
Day 57 (56 days [± 3 days] post injection, if Cycle 2 is delayed)	During visit day	During visit day	X e	X e		X e
Cycles 2 and beyond Treatment Period (until last planned cycle) with predose FPI-2053 followed by [Ac]-FPI-2068						
Day of [  Ac]-FPI-2068 administration	Predose FPI-2053 administration (within 2 h prior)	X	X	X	X	X
	End of FPI-2053 administration	+ 5 min	X			
	Predose [  Ac]-FPI-2068 administration	- 5 min	X			
	End of [  Ac]-FPI-2068 administration	+ 5 min	X			
Day 15 (14 days [± 2 days] post injection)			During visit day	During visit day		
Day 57 (56 days [± 3 days] post injection, if next cycle is delayed)			X e	X e		X e

ADA, anti-drug antibody; bsAb, bispecific monovalent antibody; CT, computed tomography; ctDNA, circulating tumour DNA; ECG, electrocardiogram; PK, pharmacokinetics; RNA, ribonucleic acid; SPECT, single-photon emission computed tomography; TCR, T-cell receptor.

a ECG may be performed, if clinically indicated, at any other visit/timepoint. ECGs must be performed prior to collection of the PK sample at the same timepoint.

b Not required initially, but if early PK data indicates that it is necessary, the 8-hour PK timepoint will be collected.

c If 8 h post injection PK sample is drawn.

d The 28 or 42-day (+ 14 day) Safety Visit only occurs if the participant does not proceed to the treatment phase (i.e., only receives FPI-2053 and [In]-FPI-2107).

e Blood samples for RNA, ctDNA, and ADA assessments at End of Treatment taken only if participant does not progress to next cycle.

**8.1.11 PK, ECG, and Biomarker Sample Timepoints: Part B – Hot-only Dose Escalation (in the Event that Results from Part A Indicate that Dose Escalation Without Pre-administration of FPI-2053 is Recommended)**

**Table 28 PK, ECG, and Biomarker Sample Timepoints: Part B, Hot-only Dose Escalation (if Applicable)**

Visit/timepoint	PK	TriPLICATE 12-lead ECG a	Blood for RNA and TCR analysis	Plasma for ctDNA analysis	ADA samples
Details in Section/Appendix	8.7.1	8.4.3	8.8.1.1	8.8.1.2	8.7.2
General Screening		During visit day		During visit day	
[In]-FPI-2107 Imaging Screening Period					
Day of [  In]-FPI-2107 administration	Predose [  In]-FPI-2107 injection (within 2 h prior)	X	X	X	X
	End of [  In]-FPI-2107 injection	+ 5 min	X		
	1 hr post injection	± 10 min	X		
	2 h post injection	± 15 min	X		
	4 h post injection	± 30 min	X		
	8 h post injection b	± 30 min c	X		
Planar scintigraphy and SPECT/CT timepoints	24 hrs (± 6 h) post injection	Within 2 h prior	X		
	48 h (± 6 h) post injection	Within 2 h prior	X		
	72-96 h (± 6 h) post injection	Within 2 h prior	X		
28-day Safety Visit d					X

Visit/timepoint	PK	TriPLICATE 12-lead ECG a	BLOOD for RNA and TCR analysis	Plasma for ctDNA analysis	ADA samples
Cycle 1 – Treatment Period [Ac]-FPI-2068					
Day of [  Ac]-FPI-2068 administration	Predose (within 2 h prior)	X	X	X	X
	End of [  Ac]-FPI-2068 injection	+ 5 min	X		
	1 hr post injection	± 10 min	X		
	2 hr post injection	± 15 min	X		
	4 h post injection	± 30 min	X		
	8 h post injection b	± 30 min c	X		
Day 8 (7 days [± 6 h] post injection)	During visit day	During visit day			X
Day 15 (14 days [± 2 days] post injection)	During visit day	During visit day	During visit day	During visit day	
Day 22 (21 days [± 2 days] post injection)	During visit day	During visit day			X
Day 29 (28 days [± 3 days] post injection)	During visit day	During visit day			
Day 57 (56 days [± 3 days] post injection, if Cycle 2 is delayed)	During visit day	During visit day	X e	X e	X e
Cycles 2 and beyond Treatment Period (until last planned cycle)					
Day of [  Ac]-FPI-2068 administration	Predose (within 2 h prior)	X	X	X	X
	End of [  Ac]-FPI-2068 administration	+ 5 min	X		
Day 15 (14 days [± 2 days] post injection)			During visit day	During visit day	

Visit/timepoint	PK	TriPLICATE 12-lead ECG a	Blood for RNA and TCR analysis	Plasma for ctDNA analysis	ADA samples
Day 57 (56 days [ $\pm$ 3 days] post injection, if next cycle is delayed)			X c	X c	X c

ADA, anti-drug antibody; CT, computed tomography; ctDNA, circulating tumour DNA; ECG, electrocardiogram; PK, pharmacokinetics; RNA, ribonucleic acid; SPECT, single-photon emission computed tomography; TCR, T-cell receptor.

a ECG may be performed, if clinically indicated, at any other visit/timepoint. ECGs must be performed prior to collection of the PK sample at the same timepoint.

b Not required initially, but if early PK data indicates that it is necessary, the 8-hour PK timepoint will be collected.

c If 8 h post injection PK sample is drawn.

d The 28 or 42-day (+ 14 day) Safety Visit only occurs if the participant does not proceed to the treatment phase (i.e., only receives [In]-FPI-2107).

e Blood samples for RNA, ctDNA, and ADA assessments at End of Treatment taken only if participant does not progress to next cycle.

## 8.2 Efficacy Assessments

### 8.2.1 Tumour Assessments

Tumour assessments will be based on RECIST v1.1 ([Eisenhauer et al, 2009](#)) and will be performed approximately every 8 weeks ( $\pm$  1 week) after the first [Ac]-FPI-2068 dose, or as clinically indicated (see Section [8.1](#)).

Standard radiographic imaging using RECIST v1.1 is used to assess both response (in participants with measurable disease) and progression. An objective response (OR) as per RECIST v1.1 criteria requires confirmation of PR and complete response (CR) and must occur no fewer than 4 weeks after initial documentation of PR or CR. Disease progression will be defined as per RECIST v1.1.

#### Tumour Evaluations

All tumour assessments should include the following evaluations: physical examination and cross-sectional imaging using computed tomography (CT) or magnetic resonance imaging (MRI) scan.

#### Physical Examination

Lesions detected by physical examination will only be considered measurable if superficial, e.g., skin nodules, and palpable lymph nodes and spleen. Documentation by colour photography including ruler is recommended for estimating the size of skin lesions.

#### Imaging

Chest, abdomen, and pelvic CT/MRI scans are required for all participants. Central nervous system (CNS) imaging is optional unless disease is known to be present at baseline.

The preferred method of systemic disease assessment is CT with contrast; if CT with contrast is contraindicated, CT without contrast is preferred over MRI. The preferred method for CNS imaging is MRI; if CT scan is performed, CT with contrast is required. The same method should be followed for all subsequent tumour assessments.

- CT scans
  - CT scans should be performed with contiguous cuts in slice thickness of 5 mm or less. Spiral CT should be performed using a 5-mm contiguous reconstruction algorithm.
  - CT scans of hepatic tumours should be collected in the hepatic arterial, portal venous, and delayed phases ([Lencioni and Llovet, 2010](#)).
- MRI scans
  - MRI scan is acceptable for measurement of lesions provided that the same anatomical plane is used for serial assessments. If possible, the same imaging device should be used for serial evaluations.

- MRI scans of hepatic tumours should be performed in the precontrast, hepatic arterial, portal venous and delayed phases ([Lencioni and Llovet, 2010](#)).

### 8.2.2 Overall Survival

Assessments for survival will be conducted every 3 months for the first 2 years then every 6 months following treatment discontinuation. Survival information may be obtained via telephone contact with the participant, participant's family, by contact with the participant's current physician, or local death registries. Additional assessments, including subsequent anticancer therapy, are to be recorded.

### 8.3 Dosimetry Assessments

Dosimetry assessments will be performed according to the SoAs (see Section [8.1](#)).

Internal dosimetry estimates will be obtained for each participant from the scintigraphy images and SPECT/CT using the Medical Internal Radiation Dose technique and the OLINDA/EXM internal dosimetry software. A total radiation dose estimate will be computed for each participant both for [In]-FPI-2107 and for [Ac]-FPI-2068 with and without FPI-2053. For [Ac]-FPI-2068, total radiation dose estimates on a per unit injected activity basis (mGy/MBq) and for the CSP-planned amount of injected [Ac]-FPI-2068 will be computed.

Participants may receive their first cycle of [Ac]-FPI-2068, with or without FPI-2053, after confirmation of successful completion of the imaging screening with [In]-FPI-2107 including organ dosimetry and sufficient target expression by the imaging vendor(s). Please refer to the imaging manual for details. All subsequent cycles of [Ac]-FPI-2068 will be based on individual dosimetry and will not exceed the participant's estimated cumulative radiation dose limit to specified organs.

The total radiation doses estimated for kidneys, liver, and lungs will be compared to published, radiation exposure data, based on ICRP prespecified limits ([Stewart et al, 2012](#)).

The critical organ radiation dose limits are kidneys  $\leq$  23 Gy (cumulative); liver  $\leq$  31 Gy (cumulative); red bone marrow  $\leq$  2 Gy (cumulative, Part A only) and lungs  $\leq$  16.5 Gy (cumulative). If any of the 4 organs' (3 organs' for Part B) estimated radiation doses (based on the planned administration) exceeds these limits, then the participant will not receive the planned full dose of [Ac]-FPI-2068. The total amount of injected activity necessary to approach but not exceed the organ dose limit will be computed. A new total radiation dose estimate will be computed for the participant using this dosimetry-limited injected activity quantity. The participant may receive this adjusted (reduced) dose of [Ac]-FPI-2068 following consultation and agreement between the Investigator, Sponsor, and Medical Monitor.

The detailed procedures for image acquisition and analysis, as well as the acquisition

timepoints, will be described in the Imaging Charter and in the Site Imaging Manual. Sponsor-identified independent radiologist(s) and physicist(s) will confirm EGFR/c-MET tumour uptake positivity and estimates of healthy organ and whole body dosimetry. These determinations will be shared with study Investigators prior to administration of each participant's first cycle of treatment.

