### 4.3.3 [Ac]-FPI-2068

The rationale for the starting dose of 15 kBq/kg is based on the estimated radiation absorbed doses to critical organs projected from the cynomolgus monkey dosimetry study with [In]-FPI-2107, in conjunction with the safety margin calculated from the NOAEL of the mass dose 5 mg/kg of FPI-2054 in cynomolgus monkeys from the GLP toxicology study (see [Table 10](#) and [Table 11](#)) and the PK projections based on the model described above.

The planned starting dose of [Ac]-FPI-2068 in mass dose terms are 200-fold lower than the NOAEL dose in a non-GLP toxicity study in non-human primates. Based on the upper end of the mass dose range, the AUC and Cmax margins to the NOAEL dose are > 100-fold (see [Table 12](#)). Furthermore, the results of a cynomolgus monkey SPECT/CT biodistribution and dosimetry study were analysed to project adult human radiation absorbed doses of [Ac]-FPI-2068. These projections suggest that the proposed starting dose of 15 kBq/kg [Ac]-FPI-2068 with or without FPI-2053 coadministration will result in per-cycle absorbed doses to the critical organs and red marrow representing margins of 2.9 and 6.3-fold, of the International Commission on Radiological Protection (ICRP) limit with higher margins to kidney, liver, and lung ICRP limits.

**Table 10** **Projected Radiation Absorbed Doses to Critical Organs Following Administration of [Ac]-FPI-2068 per Single 15 kBq/kg Dose With or Without a Saturating Dose of FPI-2053**

Organ/tissue	ICRP organ limit (Gy) a	Absorbed dose per 15 kBq/kg cycle of [  Ac]-FPI-2068 (Sv)		Margin (organ limit/absorbed dose)	
		[  Ac]-FPI-2068 b, c	[  Ac]-FPI-2068 + FPI-2053 b, d	[  Ac]-FPI-2068	[  Ac]-FPI-2068 + FPI-2053
Kidney	23	0.36	0.54	64	43
Liver	31	3.6	1.5	8.5	20
Lung	16.5	0.11	0.35	147	47
Red marrow	2	0.32	0.69	6.3	2.9

ICRP, International Commission on Radiological Protection; Sv, sievert.

a ICR Publication 118, 2012

b Assuming 70kg bodyweight and RBE = 5.

c Based on projected absorbed doses for FPI-2068 for adult human kidney = 341 mSv/MBq, liver = 3470 mSv/MBq, lung = 106 mSv/MBq, red marrow = 303 mSv/MBq.

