d Based on projected absorbed doses for FPI-2068 for adult human predosed with a saturating dose of unlabelled FPI-2053 (10 mg/kg in NHPs) kidney = 514 mSv/MBq, liver = 1430 mSv/MBq, lung = 333mSv/MBq, red marrow = 657 mSv/MBq.

**Table 11** **Projected Radiation Absorbed Doses to Critical Organs Following Administration of [Ac]-FPI-2068 Following 3 Cycles of 15 kBq/kg With or Without a Saturating Dose of FPI-2053**

Organ/tissue	ICRP organ limit (Gy) a	Absorbed dose after 3 cycles of 15 kBq/kg [  Ac]-FPI-2068 (Sv)		Margin (organ limit/absorbed dose)	
		[  Ac]-FPI-2068 b, c	[  Ac]-FPI-2068 + FPI-2053 b, d	[  Ac]-FPI-2068	[  Ac]-FPI-2068 + FPI-2053
Kidney	23	1.1	1.6	21	14
Liver	31	11	4.5	2.8	6.8
Lung	16.5	0.34	1.0	49	15
Red marrow	2	0.95	2.1	2.1	0.97

ICRP, International Commission on Radiological Protection; Sv, sievert.

a ICR Publication 118, 2012

b Assuming 70kg bodyweight and RBE = 5.

c Based on projected absorbed doses for FPI-2068 for adult human kidney = 341 mSv/MBq, liver = 3470 mSv/MBq, lung = 106 mSv/MBq, red marrow = 303 mSv/MBq.

d Based on projected absorbed doses for FPI-2068 for adult human predosed with a saturating dose of unlabelled FPI-2053 (10 mg/kg in NHPs) kidney = 514 mSv/MBq, liver = 1430mSv/MBq, lung = 333mSv/MBq, red marrow = 657 mSv/MBq.

**Table 12** [Ac]-FPI-2068 Safety Margins According to Mass Dose Range

[  Ac]-FPI-2068 mass dose range (kBq/kg)	[  Ac]-FPI-2068 mass dose range (μg/kg)	AUC cyno (μg hr/mL)	AUC cyno (μg d/mL)	Predicted human AUC lower (μg d/mL)	Predicted human AUC upper (μg d/mL)	Safety margin a (AUC cyno / AUC h )	C max, cyno (μg/mL)	Predicted human C max, lower (μg/mL)	Predicted human C max, upper (μg/mL)	Safety margin a (C max, cyno / C max, h )
15	4.5-37.5	6360	265	0.15	1.3	200	89.4	0.11	0.84	106
25	7.5-62.5			0.25	2.2	120		0.18	1.4	63
40	12-100			0.40	3.5	75		0.28	2.3	39
70	21-175			0.70	6.2	43		0.49	3.9	22

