AUC, area under the curve; AUCcyno, area under the curve in cynomolgus monkey; AUCh, area under the curve in human; Cmax, maximum concentration after dosing; Cmax, cyno, maximum concentration after dosing in cynomolgus monkey; Cmax, h, maximum concentration after dosing in human; Cmax, lower, maximum concentration after dosing lower limit; Cmax, upper, maximum concentration after dosing upper limit; GLP, Good Laboratory Practice. PK, pharmacokinetics.

a Margins calculated based on upper limit of mass dose range

Mass dose range of [Ac]-FPI-2068 based on manufacturing target specific activity range of 0.814-3.145 MBq/mg and a 10-day shelf-life. AUC and Cmax of FPI-2054 from cynomolgus monkey based on Day 1 PK profiles from a 5 week GLP toxicology Study 1589.04 (IV bolus).

Prior to treatment with [Ac]-FPI-2068, participants will be imaged with [In]-FPI-2107 (with and/or without predose administration of FPI-2053) to determine participant eligibility per local review. Prior to the administration of [Ac]-FPI-2068, individual dosimetry assessments and tumour-to-background-ratio (TBR) will be conducted centrally and reviewed with the Investigator to confirm eligibility and estimate the maximum allowable cycles of [Ac]-FPI-2068. All subsequent cycles of [Ac]-FPI-2068 will be based on assigned dose level and individual dosimetry such that an individual participant's cumulative radiation absorbed dose will not exceed limits of 23 Gy for kidneys, 31 Gy for liver, 16.5 Gy for lungs, and for Part A only, 2 Gy for red bone marrow. If a participant reaches a cycle in which the planned administered dose exceeds prespecified individualised cumulative radiation dose limits, the participant may receive a reduced administration such that the specified cumulative limit is not reached.

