### Prior/Concomitant Therapy

- 8 Prior systemic radiopharmaceutical therapy.
- 9 Anti-cancer therapy, such as chemotherapy, immunotherapy, hormonal therapy, targeted therapy, or investigational agents within five half-lives or 4 weeks, whichever is shorter, prior to administration of the first dose of [In]-FPI-2107:
  - a) Ongoing toxicities from prior treatment(s) must have resolved to  $\leq$  CTCAE Grade 1, except for alopecia.
  - b) Concurrent systemic high-dose corticosteroids (in dosing exceeding 10 mg once a day of prednisone or equivalent) is excluded except when used intermittently in an antiemetic regimen, or as part of a premedication regimen.

10 External beam radiation therapy (EBRT) within 28 days prior to the first dose of [In]-FPI-2107:

- Prior EBRT limits must not have exceeded 1.7 Gy to the kidney, 17 Gy to the liver, and 0.5 Gy to the lung. The projected total absorbed dose to the kidney, liver, lung, and red bone marrow, when added to the previous cumulative dose for those organs, will not exceed the individual organ limits, as defined in Section 4.3.
- Prior radiation > 20 Gy to more than one-third of the pelvis.

11 Major surgical procedure within 28 days prior to administration of the first dose of [In]-FPI-2107:

12 \*Received any type of vaccine (e.g., live, live-attenuated, killed, viral vector or messenger RNA [mRNA] vaccine) within 30 days prior to the first dose of FPI-2053 or [In]-FPI-2107.

\* Killed, viral vector, and mRNA vaccines may be allowed after completion of the DLT-period upon agreement between the Investigator, Sponsor, and Medical Monitor.

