##### [Ac]-FPI-2068

For Part A (first radiation dose level, 15 kBq/kg with and without unlabelled bsAb), dosimetry estimates of all previous and planned therapeutic administrations of [Ac]-FPI-2068 do not exceed a cumulative exposure of 23 Gy for kidneys, 31 Gy for liver, 2 Gy for red bone marrow, and 16.5 Gy for lungs. Additionally, the absorbed radiation dose to the kidneys, liver, and lungs from prior EBRT treatment must be taken into account and considered part of the cumulative dose to the organs when determining the number of cycles of treatment that a participant can receive. Eligible participants will receive up to 3 cycles of [Ac]-FPI-2068.

For Part B, dosimetry estimates of all previous and planned therapeutic administrations of [Ac]-FPI-2068 do not exceed a cumulative exposure of 23 Gy for kidneys, 31 Gy for liver, and 16.5 Gy for lungs. The absorbed radiation dose to the kidneys, liver, and lungs from prior EBRT treatment must be taken into account and considered part of the cumulative dose to the organs when determining the number of cycles of treatment that a participant can receive.

Eligible participants will receive up to 3 cycles of [Ac]-FPI-2068.

If a planned dose level exceeds the total allowable cumulative dose, the participant may receive a reduced dose.

The dose level of [Ac]-FPI-2068 will be determined by the assigned dose level (see [Table 7](#) and [Table 8](#)).

The volume to be administered to a given participant should be calculated using the:

- participant's body weight (kg)
- dosage level (in kBq/kg body weight)
- radioactivity concentration of the product at time of calibration (the activity concentration at time of calibration and the date of calibration are provided on the vial and lead pig label)

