**Table 13** **Investigational Products**

Intervention name	[  In]-FPI-2107	FPI-2053	[  Ac]-FPI-2068
Type	Biologic	Biologic	Biologic
Dose formulation	Solution for injection	Concentrate for infusion	Solution for injection
Unit dose strength(s)	74–111 MBq/mL (at time of calibration)	100 mg/vial	0.407–0.629 MBq/mL (at time of calibration)
Dosage level(s)	185 MBq (5 mCi) a, b	Proposed 0.3, 1, and 3 mg/kg Q8W c	Proposed 15, 25, 40, and 70 kBq/kg Q8W b
Route of administration	IV injection	IV infusion	IV injection
Use	Experimental	Experimental	Experimental
IMP or NIMP	IMP	IMP	IMP
Sourcing	Provided centrally by the Sponsor	Provided centrally by the Sponsor	Provided centrally by the Sponsor
Packaging and labelling	Study intervention will be labelled in accordance with GMP Annex 13 and per country regulatory requirement	Study intervention will be labelled in accordance with GMP Annex 13 and per country regulatory requirement	Study intervention will be labelled in accordance with GMP Annex 13 and per country regulatory requirement
Aliases	None	None	None

GMP, Good Manufacturing Practice; IMP, investigational medicinal product; IND, investigational new drug; IV, intravenous; NIMP, non-IMP; Q8W, every 8 weeks.

a [In]-FPI-2107 is only given during the imaging screening period. All participants will receive 2 doses of [In]-FPI-2107 unless the optimal dose of FPI-2053 from Part A is 0, in which case participants in Part B will receive one dose.

b Administered dose tolerances for [In]-FPI-2107 and [Ac]-FPI-2068 are outlined in the Pharmacy Manual.

c The proposed FPI-2053 dose levels of 0.3, 1, and 3 mg/kg will be used in Part A. The FPI-2053 dose level in Part B will be determined in Part A.

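### The organ-limit gate compares actinium-225 dose with Gy limits without stating an RBE, although Tables 10 and 11 justify the same limits with RBE = 5-weighted doses

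*Protocol*

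**What the plan says.** Protocol Section 8.3 derives each participant's actinium-225 dose from indium-111 imaging. It asks for "total radiation dose estimates on a per unit injected activity basis (mGy/MBq" and also for the dose at the planned activity. If an organ estimate exceeds its limit, the full activity is not given; a reduced activity that stays within the limit is computed and may be given instead.

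The limits recur in three other places, always in Gy and with no mention of weighting:

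- Section 4.3.3: "cumulative radiation absorbed dose will not exceed limits of 23 Gy for kidneys, 31 Gy for liver", with 16.5 Gy for lung and, in Part A only, 2 Gy for marrow.
- Section 6.1.1.2: planned and past administrations "do not exceed a cumulative exposure of 23 Gy for kidneys, 31 Gy for liver, 2 Gy for red bone marrow" in Part A; Part B drops the marrow limit. Prior external-beam dose to kidney, liver and lung counts towards the total.
- Table 15 in Section 6.7.3 repeats both the limits and the external-beam rule.

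The justification for these limits is in Tables 10 and 11 of Section 4.3.3. Footnote b reads "Assuming 70kg bodyweight and RBE = 5", footnote c "Based on projected absorbed doses for FPI-2068 for adult human kidney = 341 mSv/MBq, liver = 3470 mSv/MBq", and Table 11 heads its Sv columns "Absorbed dose after 3 cycles of 15 kBq/kg". Each margin is a limit in Gy divided by a dose in Sv. RBE appears only in these footnotes.

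**The concern.** The gate decides whether a participant receives the full activity and how many cycles are allowed. Table 5 cites it as mitigation for marrow, liver, lung and renal toxicity. A dosimetrist who takes Section 8.3 at face value would compare unweighted alpha dose with limits whose safety margins were worked out on weighted dose, and would add photon dose from earlier radiotherapy to that unweighted figure. The error would run in the permissive direction. The question is how far the two scales differ and where the difference would change a dose.

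**Working it through.** **Inputs**

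- Coefficients in mSv/MBq, no predose / saturating predose (footnotes c and d to Tables 10 and 11): kidney 341 / 514, liver 3470 / 1430, lung 106 / 333, red marrow 303 / 657.
- 70 kg and RBE = 5 (footnote b).
- Activity levels 15, 25, 40 and 70 kBq/kg (Tables 7 and 8), up to three cycles. At 70 kg these are 1.05, 1.75, 2.8 and 4.9 MBq per cycle.
- Limits: kidney 23, liver 31, lung 16.5, marrow 2 (Part A only).
- Largest prior external-beam dose allowed by exclusion criterion 10: "Prior EBRT limits must not have exceeded 1.7 Gy to the kidney, 17 Gy to the liver, and 0.5 Gy to the lung".

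**Step 1: reproduce the protocol's figures.** Dose = coefficient × MBq × cycles.

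- Marrow, saturating predose: 657 × 1.05 = 690 mSv = 0.69 Sv per cycle; three cycles 2.07 Sv (Table 11: 2.1). Margin 2 / 2.07 = 0.97, as stated.
- Liver, no predose: 3470 × 1.05 = 3.64 Sv; three cycles 10.9 Sv (Table 11: 11).

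No further factor of five is needed, so the mSv/MBq coefficients already contain the RBE.

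**Step 2: the literal reading.** If all the dose is alpha, the unweighted value is the weighted value divided by 5. If a fraction f of the absorbed dose is alpha, the ratio is 1 + 4f. The protocol gives no f. Assuming 0.8 to 1.0, the ratio is 4.2 to 5.0.

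**Step 3: where the two readings give different dosing** (three cycles; unweighted column uses ratio 5)

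| Case | Weighted | Unweighted | Limit |
|---|---|---|---|
| Liver, hot-only, 70 kBq/kg, no prior radiotherapy | 3 × 3470 × 4.9 = 51.0 | 10.2 | 31 |
| Liver, hot-only, 25 kBq/kg, 17 Gy prior | 17 + 3 × 6.07 = 35.2 | 17 + 3 × 1.21 = 20.6 | 31 |
| Liver, saturating predose, 70 kBq/kg, 17 Gy prior | 17 + 3 × 7.01 = 38.0 | 17 + 3 × 1.40 = 21.2 | 31 |
| Marrow, Part A, saturating predose | 2.07 | 0.41 | 2 |

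- *Row 1.* Weighted totals are 17.0, 34.0 and 51.0. The room left for cycle 2 is (31 − 17.0) / 17.0 = 0.82, so cycle 2 is cut by 18% and cycle 3 is barred. Unweighted totals of 3.4, 6.8 and 10.2 allow three full cycles. At ratio 4.2 the unweighted total is 12.1, still well under 31.
- *Rows 2 and 3.* The weighted gate binds only when prior liver dose exceeds 31 − 3 × 6.07 = 12.8 Gy at 25 kBq/kg without predose, or 31 − 21.0 = 10.0 Gy at 70 kBq/kg with saturating predose. The same arithmetic for hot-only 40 kBq/kg gives 31 − 29.15 = 1.85 Gy. At 17 Gy prior dose, row 2 leaves room for (31 − 29.15) / 6.07 = 0.31 of cycle 3, a cut of 69%.
- *Row 4.* The weighted limit binds only above 2 / (3 × 1.05) = 0.635 Sv/MBq, or 635 mSv/MBq, which is 94% of the way from 303 to 657. At 657 the room for cycle 3 is (2 − 1.38) / 0.69 = 0.90, a cut of about 10%. Without predose the totals are 0.95 weighted and 0.19 unweighted. At ratio 4.2 the saturated unweighted total is 0.49.

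**Step 4: where nothing changes.** Weighted maxima at 70 kBq/kg over three cycles:

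- Kidney: 3 × 514 × 4.9 = 7.6, or 9.3 with 1.7 Gy prior dose, against 23.
- Lung: 3 × 333 × 4.9 = 4.9, or 5.4 with 0.5 Gy prior dose, against 16.5.
- Liver without prior radiotherapy: hot-only up to 40 kBq/kg (29.1), and saturating predose at every planned level (21.0 at 70 kBq/kg).
- Liver with 17 Gy prior: hot-only at 15 kBq/kg (17 + 10.9 = 27.9), and saturating predose at 40 kBq/kg (17 + 12.0 = 29.0).

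**Step 5: which scale was intended?** The weighted no-predose coefficients at 4.9 MBq give 1.67, 17.0 and 0.52. These match the external-beam caps of 1.7, 17 and 0.5 Gy; the unweighted values (0.33, 3.4, 0.10) do not. That the caps were derived this way is an inference, but it points to weighted dose.

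**The case against.** The other side has four good points.

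- Section 4.1.4 sends the reader to 4.3.3 for the dose limits, and 4.3.3 contains the RBE footnotes. The protocol also calls its Sv columns absorbed dose and divides Gy limits by them, so Gy here does not reliably mean unweighted.
- The unit mGy/MBq in 8.3 describes one output. The gate sentence itself refers to the dose for the planned administration. A per-activity absorbed dose can be a correct intermediate quantity that is weighted later. Absorbed dose is also a primary endpoint (Table 6), and the tumour criteria of under 5 Gy (4.1) and at least 25 Gy (4.1.1) are stated in Gy.
- Dosimetry is done centrally and checked by independent physicists, with procedures left to the Imaging Charter and Site Imaging Manual. Those documents may fix the RBE.
- The conditions under which it matters are narrow. Table 8 lists zero predose only at 15 kBq/kg, and hot-only escalation arises only if the Part A optimum is zero. Table 13, footnote a, provides for this: participants have two imaging doses "unless the optimal dose of FPI-2053 from Part A is 0".

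All four limit the point. A reader might infer that 8.3 carries a wrong unit that should be replaced, or that the sponsor deliberately set a laxer gate; the documents support neither. What remains is that 8.3, 6.1.1.2 and Table 15 give the rule and its unit with no conversion step, and the rule in 4.3.3 does not say that the table footnotes govern it. The text shown does not say that the imaging documents set the RBE.

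**Conclusion.** The inconsistency is on the page and should be corrected. As written, the gate can be read on a scale up to five times laxer than the one that justifies its limits (4.2 to 5.0 times if 80 to 100% of the dose is alpha, an assumed range). On the literal reading no organ limit binds at any planned level, even with the largest permitted prior liver dose (17 + 10.2 = 27.2 against 31).

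The effect on dosing is limited to hot-only liver at 70 kBq/kg, liver with prior radiotherapy above the thresholds shown, and Part A marrow close to saturating predose, where the loss is at most about 10% of cycle 3. These results assume a 70 kg participant, the protocol's projections from monkey imaging, and no earlier marrow dose. Individual uptake will differ.

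It cannot be concluded that any participant would be overdosed. If the central dosimetry is already weighted, only the text is at fault. Confidence in the mismatch is high; confidence that it would reach a participant's dose is moderate at most.

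**What to change.** Keep mGy/MBq in Section 8.3 as the reported absorbed-dose output, and leave the tumour-dose criteria in Gy. Add one rule to 8.3: for the organ-limit gate, actinium-225 organ doses are weighted with RBE = 5, as in Tables 10 and 11, before prior external-beam dose is added and before comparison with the 23, 31, 16.5 and (Part A) 2 limits. Label those limits as RBE-weighted. Add a cross-reference to this rule in 4.3.3, 6.1.1.2 and Table 15, and check that the Imaging Charter and Site Imaging Manual agree.

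The cost is wording in four places, with no extra participants, scans or visits. If dosimetry is already weighted, no dose changes.
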